8.3.16. Evaluation of Biomarkers

A single buccal swab sample for evaluation of PNPLA3/other genetic biomarkers will be collected pre-dose on Day 1.

8.3.17. Lipid Lowering Therapy Assessment

LDL-C will be evaluated at all study visits beginning at Week 2 for possible increases in lipid levels associated with aldafermin administration. Rosuvastatin will be used to manage cholesterol levels and initiated if protocol-defined lipid management criteria are met.

Rosuvastatin and matched placebo are over-encapsulated and provided in multi-capsule bottles ([Section 6.2.1.2](#)). Initiation and ongoing dose adjustments of rosuvastatin will be managed by a third-party Medical Monitor who is blinded to treatment assignment but unblinded to LDL-C values and related safety laboratory results. Rosuvastatin dose changes will be managed through the IxRS. Lipid levels and titration recommendations will be blinded to the sponsor, sponsor's Medical Monitor, investigators, subjects, and site. Initiation and dose adjustments will be determined by the lipid levels collected at Week 2 through Week 54, with lipid levels at Day 1 serving as baseline. LDL-C samples will be analyzed and reported to the third-party Medical Monitor. A kit containing rosuvastatin or matched placebo bottles will be assigned as instructed through the IxRS system and based on subjects LDL-C level assessment at each study visit from Week 2 through Week 42 (statin-naïve) or Week 48 (statin-experienced), and will be delivered to subjects via a courier service vendor ([Section 6.1.3.1](#)). The site will communicate to the subject the assigned bottle(s) and dosing should be immediately initiated.

Group A

Statin-experienced subjects (definition from Exclusion Criteria 9b) will be switched to an equivalent intensity rosuvastatin dose (high intensity dose – 20 mg rosuvastatin, moderate intensity dose – 10 mg rosuvastatin, low intensity dose – 5 mg rosuvastatin). For subjects who are self-identified Asians, the high intensity rosuvastatin dose is 10 mg, and the moderate intensity rosuvastatin dose is 5 mg. The treatment goal for this group of statin-experienced subjects is LDL-C level of ≤ 70 mg/dL (1.8 mmol/L) or $\geq 50\%$ LDL-C reduction from the Week 2 level, starting at Week 6.

Group B

Subjects who are statin-naïve (definition from Exclusion Criteria 9a) AND who have risk-enhanced diagnoses (e.g., clinical ASCVD, CVA) AND LDL-C level of >70 mg/dL (1.8 mmol/L) will initiate over-encapsulated rosuvastatin at 5 mg daily with a treatment goal of LDL-C level of ≤ 70 mg/dL (1.8 mmol/L) or $\geq 50\%$ LDL-C reduction from the Week 2 level. Those subjects who are already at LDL-C level of ≤ 70 mg/dL (1.8 mmol/L) will initiate over-encapsulated rosuvastatin placebo, and LDL-C initiation criteria will be re-evaluated at subsequent clinic visits (i.e., Week 6, 12, 18, 24, 30, 36, 42).

Group C

Statin-naïve subjects without risk-enhanced diagnoses AND with a 10-year ASCVD risk $\geq 7.5\%$ (US) $>1\%$ (Europe) will initiate over-encapsulated rosuvastatin at 5 mg daily.

The treatment goal is LDL-C level of ≤ 70 mg/dL (1.8 mmol/L) or $\geq 50\%$ LDL-C reduction from the Week 2 level.

Statin-naïve subjects without risk-enhanced diagnoses AND with a 10-year ASCVD risk $<7.5\%$ will initiate over-encapsulated rosuvastatin placebo. ASCVD risk and LDL-C laboratory assessment will be evaluated at subsequent clinic visits (i.e., Week 6, 12, 18, 24, 30, 36, 42) in order to determine whether rosuvastatin should be initiated at 5 mg daily.

All Subjects

At subsequent clinic visits, subjects who have achieved the protocol-defined LDL-C treatment goal will continue on their most recent assigned dose of rosuvastatin/placebo. If a subject fails to achieve the determined LDL-C goal despite increasing the rosuvastatin dose, those subjects will be reassigned to the lowest dose used to achieve the current LDL-C level.

Subjects on the maximum dose of rosuvastatin 40 mg whose LDL-C levels are still not at the protocol-defined LDL-C goal will continue on the study with rosuvastatin 40 mg unless the subject experiences a cardiovascular-related SAE (e.g., myocardial infarction, CVA).

All subjects will be assessed at Weeks 49 and 54 to confirm their LDL-C levels have either decreased to near baseline or at the protocol-defined LDL-C goal. At that point, no additional follow-up will be performed.

Subjects who do not meet criteria at Week 54 (Day 1 levels within 15 mg/dL or at the protocol-defined LDL-C goal) will have an additional 4-week follow-up visit at Week 58 to confirm that their LDL-C level returned to near baseline. At this point, the third-party Medical Monitor may recommend specific follow-up with the subject's regular physician. Otherwise, all subjects should be advised to follow-up with their regular physician regarding any lipid management needs going forward.

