
| Synopsis | Study 282-CC-207 |
|--|--|
| | All subjects will be assessed at Weeks 49 and 54 to confirm their LDL-C levels have either decreased to near baseline, at which point no additional follow-up is needed. Subjects who do not meet LDL-C decrease criteria at Week 54 will have an additional 4-week follow-up visit at Week 58 to confirm that their LDL-C level returned to near baseline. Subjects may remain on statin through Week 58. |
| | As part of safety monitoring, subjects will undergo ultrasound and alpha fetoprotein (AFP) testing at Weeks 24 and 48 to screen for HCC. Subjects with new lesions ≥ 10 mm with AFP >20 ng/mL will be treated according to local guidelines. If new lesions ≥ 10 mm with AFP >20 ng/mL occur at Week 24, subjects may continue on study drug at the discretion of the investigator unless or until a clinical diagnosis of HCC is made (defined as LI-RADS 4 or 5 on MRI, or histological confirmation of HCC). For subjects with suspected HCC by ultrasound and AFP screening, additional imaging may be obtained, and data will be gathered for adjudication. |
| | Safety will be monitored by a data safety monitoring board (DSMB). |
| | All subjects will return to the clinic for the End-of-Treatment (EOT) visit at Week 48. Subjects will return to the clinic at Weeks 49 and 54 (or at 1 and 6 weeks after last dose of aldafermin) for a post-treatment response and End-of-Study (EOS) follow-up visits. |
| | Subjects may be contacted to participate in additional optional follow-up visits, if necessary, to monitor anti-drug antibody (ADA) response. |
| Number of Subjects: | Up to approximately 150 eligible subjects will be randomized |
| Number of Study Sites: | This is a global study planned in approximately 80 sites |
| Test Product, Dose, and Mode of Administration: | The investigational product is aldafermin, which will be administered once daily by subcutaneous injection. Subjects will receive 0.3 mg aldafermin, 1 mg aldafermin, 3 mg aldafermin, or matched placebo. Under protocol Version 5.0 and subsequent versions, randomization to the 0.3 mg aldafermin dose was discontinued. |

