| | Rosuvastatin will be administered for subjects meeting pre-specified criteria at Week 2 with dose optimization opportunities at Weeks 6, 12, 18, 24, 30, 36, and 42. Subjects who do not meet dose escalation criteria will continue on their prior assigned dose of rosuvastatin/placebo. Study-labeled rosuvastatin/matched placebo is over-encapsulated and will be supplied in either 5 mg, 10 mg, 20 mg, or 40 mg total daily doses as outlined in Section 6.2.1.2 of the protocol to manage possible LDL-C increase during aldafermin treatment. |

| Synopsis | Study 282-CC-207 |
|---|---|
| Duration of Treatment and Study: | 
Total study-drug treatment: 48 weeks.
 
Total study duration: up to 74 weeks.
 
Subjects will review and sign the Informed Consent Form at the Day 56 Screening Visit and will undergo screening assessments to verify eligibility for the study for up to 8 weeks (up to 16 weeks with Medical Monitor approval) from the date of consent. All subjects will be treated with aldafermin or matched placebo for 48 weeks and will be monitored for additional 6-10 weeks after completing their final dose of aldafermin or matched placebo.
 
The total duration of individual subject participation, including screening (up to 8 weeks [up to 16 weeks with Medical Monitor approval]), the treatment period (48 weeks) and the safety follow-up (6-10 weeks) will be up to 74 weeks.
 |

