Over-encapsulated rosuvastatin will be initiated at Week 2, starting at 5 mg QD in statin-naïve subjects whose ASCVD 10-year risk score is $\geq 7.5\%$ (US) or \geq moderate level risk (European), [Appendix 4](#). In subjects who are statin-naïve with diabetes or a history of myocardial infarction or stroke, or other ASCVD risk-enhancing diagnoses, rosuvastatin will be initiated at 5 mg at Week 2 if LDL-C is not already at the goal of ≤ 70 mg/dL (1.8 mmol/L). Though there is incremental cardiovascular benefit to additional LDL-C lowering ([Sabatine 2018](#)), other reports, including the meta-analysis by Ma, et al. suggest an association between low LDL-C levels and hemorrhagic stroke ([Ma 2019](#)), and overall, controversy remains regarding the long-term safety of medications that can help achieve low LDL-C levels such as PCSK9 inhibitors ([Pasta 2020](#), [Bandyopadhyay 2018](#)). Thus, for safety considerations, statin-naïve subjects with risk-enhancing diagnoses who are already at an LDL-C treatment goal of ≤ 70 mg/dL (1.8 mmol/L) will be initiated on over-encapsulated rosuvastatin placebo. At subsequent clinic visits, lipid levels will be evaluated and treatment with over-encapsulated rosuvastatin may be initiated or placebo may be continued.

Subjects who are statin-experienced (i.e., on statin concomitant medication), will be switched to an equivalent intensity rosuvastatin dose at Week 2. For self-identified Asians, 10 mg is

considered a high intensity dose, and 5 mg is considered a moderate intensity dose. Matched placebo will be given to statin-naive study subjects who do not meet initiation criteria at Week 2 or subsequent visits.

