8.2.4. Week 2 Procedures

Subjects will report to clinic fasted and not dosed with aldafermin. The following procedures will be performed:

Pre-dose:

- Measure vital signs (including temperature, respiratory rate, and seated blood pressure and pulse)
- Record concomitant medications
- Record AEs
- Obtain blood for 10-hour fasted clinical laboratory samples
 - Chemistry, including creatine kinase.
 - CBC
 - INR
 - Lipid panel
 - Lipoprotein particles
 - C4
 - PK
 - ADAs
 - NAbs
 - Exploratory Plasma biomarker #1

- Exploratory Plasma biomarker #2
- Exploratory Serum biomarker #3

Results for ALT, AST, Total Cholesterol, LDL, HDL, and triglycerides are blinded to the site and sponsor.

- Obtain urine sample for:

Pre-dose urine pregnancy in all female subjects of childbearing potential

In-clinic dosing and dispensing:

- Collect old aldafermin study drug kit and diary and conduct reconciliation
- Dispense new aldafermin study drug kit and diary
- Rosuvastatin/ matched placebo diary. Inform Subjects that they will be contacted in a few days regarding the delivery or pick up of their rosuvastatin/placebo drug bottles.
- Oversee subject's aldafermin study drug self-administration (from new kit)
- Perform LISSA evaluation

Before clinic discharge:

- Remind subject to bring study drug kit and diary at the next visit and not to self-administer aldafermin/placebo at home on clinic visit days
- Schedule Week 6 visit

Lipid Lowering Therapy Assessment:

The third-party Medical Monitor will evaluate LDL-C results to assess the need for lipid lowering therapy (refer to [Section 8.3.17](#)).

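### Section 8.3.17, Group C: a European statin-naive subject without risk-enhanced diagnoses and with 10-year ASCVD risk above 1% but below 7.5% meets both the rosuvastatin 5 mg rule and the placebo rule

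*Protocol*

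**What the plan says.** Section 8.3.17 divides subjects into Groups A to C for lipid management. Group C covers statin-naive subjects without risk-enhanced diagnoses and contains two rules.

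- **Rule 1 (active).** The threshold is a 10-year ASCVD risk of at least 7.5% for the US and above 1% for Europe. The sentence ends: "Europe) will initiate over-encapsulated rosuvastatin at 5 mg daily".
- **Rule 2 (placebo).** Subjects of the same kind with risk below 7.5%, no region named, "will initiate over-encapsulated rosuvastatin placebo. ASCVD risk and LDL-C laboratory assessment will be evaluated at subsequent clinic visits", to decide whether 5 mg should then be started.

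Four other places bear on the meaning:

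- The opening of Section 8.3.17 says rosuvastatin is "initiated if protocol-defined lipid management criteria are met".
- The synopsis, under test product, says: "Rosuvastatin will be administered for subjects meeting pre-specified criteria at Week 2".
- Section 4.1 gives Europe its own start criterion, at least "moderate level risk (European"), next to 7.5% for the US. It reserves matched placebo for statin-naive "study subjects who do not meet initiation criteria at Week 2 or subsequent visits". The synopsis repeats both statements.
- The Week 2 procedures (Section 8.2.4) say the third-party "Medical Monitor will evaluate LDL-C results to assess the need for lipid lowering therapy (refer to" Section 8.3.17). Later visits repeat this.

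**The concern.** Rule 2 reads as the complement of Rule 1, but it complements only the US part. Europe has a lower start threshold, so the single 7.5% cut-off overlaps the European active range. In that overlap the protocol tells the Medical Monitor to start both active drug and placebo.

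The matter at stake is background treatment and safety, not the efficacy analysis. The statin programme exists to manage possible LDL-C rises on aldafermin. Section 6.4.1 prohibits non-statin lipid-lowering agents throughout, and any statin other than study rosuvastatin from Week 2. If Rule 2 is followed literally, a European subject in the overlap is denied at Week 2 a statin that Rule 1 starts, and has no permitted alternative outside the study supply. Sites and sponsor are blinded to lipid values and to the rosuvastatin/placebo allocation, so they are poorly placed to notice a wrong assignment.

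The study is not confined to the US: "This is a global study planned in approximately 80 sites", and the protocol itself writes a European threshold.

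**Working it through.** The plan states no figure to reproduce. The check is whether the two rules assign each subject exactly once.

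**Inputs** (Section 8.3.17, Group C), with *r* the subject's own 10-year ASCVD risk in percent:

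- Active: *r* ≥ 7.5 (US); *r* > 1 (Europe).
- Placebo as written: *r* < 7.5 (any region).
- Placebo as corrected: the regional active criterion is not met, that is *r* < 7.5 (US) or *r* ≤ 1 (Europe).

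Each subject's own value is tested against both rules, so no conversion between US and European risk scales is needed.

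| *r* (%) | US, as written | Europe, as written | Europe, corrected |
|---|---|---|---|
| 0.5 | placebo | placebo | placebo |
| 1.0 | placebo | placebo | placebo |
| 1.01 | placebo | **active and placebo** | active |
| 3 | placebo | **active and placebo** | active |
| 5 | placebo | **active and placebo** | active |
| 7.49 | placebo | **active and placebo** | active |
| 7.5 | active | active | active |
| 10 | active | active | active |

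For the US, the rules are exclusive and exhaustive. For Europe, they overlap exactly where 1 < *r* < 7.5. The corrected rule leaves the US column unchanged, and every tested value in either region then meets one rule only.

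**Which rule is the wrong one.** Section 4.1 and the synopsis make placebo the residual category: it goes to statin-naive subjects who fail the initiation criteria. A European subject at 3% meets the Section 8.3.17 initiation criterion and so falls outside that category. Both general statements, that rosuvastatin is started or given when criteria are met, point the same way. Conversely, if Rule 2 prevailed, everyone below 7.5% would start on placebo in both regions, and the European threshold of 1% would have no effect. Rule 1 is therefore the intended rule, and Rule 2 lacks its regional limit.

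**The case against.** The strongest reply is that the protocol names Appendix 4 as the specific dosing algorithm, and its content is not visible in the copy reviewed. Decisions are made by one third-party Medical Monitor through the IxRS, not by sites interpreting the text separately. Whether anyone would actually be misassigned may depend on material that cannot be checked. This stands as a limit on the practical consequence. It does not rescue the sentence: the visit procedures send the monitor to Section 8.3.17, and a correct appendix would simply contradict it.

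A second reply is that intent is plain from Section 4.1, so only a region label is missing. The intent is indeed plain, but that identifies the repair and leaves the opposite instruction in place.

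Third, the harm is bounded. Affected subjects had taken no statin for at least 3 months before Screening, so no existing therapy is withdrawn, and those started on placebo are re-evaluated from Week 6 through Week 42. This is fair, although the placebo sentence gives no separate threshold for the later decision, so the same ambiguity can recur.

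Fourth, Section 4.1 expresses the European criterion as a risk level and Section 8.3.17 as a percentage. The protocol does not show that the two coincide at the boundary. This also stands, and should be confirmed when the sentence is amended.

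**Conclusion.** The concern holds: the placebo sentence in Group C is wrong as written for Europe. It contradicts the rule before it for every European Group C subject above 1% and below 7.5%, and is correct for the US.

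The number affected cannot be derived from the protocol. It is probably small, because Section 4.1 handles statin-naive subjects with diabetes under the separate risk-enhancing rule. The effect is confined to background statin assignment and safety in those subjects. Study rosuvastatin can still be started at a later visit. No between-arm bias, effect on the ELF analysis or actual inconsistent exposure is claimed.

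The conclusion rests on the Group C thresholds as printed; nothing is assumed about the content of Appendix 4. The sponsor should correct it: this is a treatment-assignment threshold in the section the Medical Monitor is told to use.

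**What to change.** Replace the opening of the placebo rule in Group C with:

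*Statin-naive subjects without risk-enhanced diagnoses who do not meet the above regional initiation criterion (i.e., <7.5% in the US; ≤1% in Europe) will initiate over-encapsulated rosuvastatin placebo.*

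This follows the residual logic of Section 4.1 and the synopsis. It adds no new cut-off, since at or below 1% is the complement of the European threshold already in Group C. At the same time, check that Appendix 4 and the IxRS specification use these cut-offs, and confirm that the European risk level named in Section 4.1 corresponds to the percentage in Section 8.3.17.

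The cost is one sentence in the next amendment and a document check.

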8.3.18. Diet and Activity Control

Subjects should maintain their normal level of physical activity, diet, and lifestyle throughout the entire study (i.e., will not begin a new exercise program or participate in any unusually strenuous physical exertion). For subjects enrolled in the optional PK sub-study, participants may be domiciled during dosing and 24-hour sampling and receive a standardized diet at scheduled times that do not conflict with other study-related activities.

8.3.19. MRI, CT, and Ultrasound for HCC Testing

As part of safety monitoring, subjects will undergo liver imaging and AFP testing to screen for HCC, followed by liver ultrasound and AFP testing at Weeks 24 and 48 for surveillance. Lesions detected on ultrasound at 24 weeks or 48 weeks, without significant change in AFP levels, will be managed according to the SOC at the clinical site. Subjects with an AFP level >20 ng/mL at either Week 24 or 48, without detectable lesions on ultrasound, will be managed according to the SOC at the clinical site. Subjects with a lesion ≥ 10 mm detected on ultrasound at 24 weeks with an AFP level >20 ng/mL at 24 weeks may continue on study drug at the discretion of the investigator unless or until a clinical diagnosis of HCC is made (defined as LI-RADS 4 or 5 at MRI, or histological confirmation of HCC). Abnormal readings with an AFP test results or suspicious ultrasound lesions will have follow-up and adjudication as defined by the Hepatocellular Carcinoma Adjudication Charter (see [Section 8.5.2](#)).

8.3.20. Evaluation of Biomarkers

Blood samples will be collected for evaluation of exploratory biomarkers 1, 2, and 3, as outlined in [Table 8](#).

8.4. Safety and Other Assessments

8.4.1. Definition of Adverse Events

An AE is defined as any untoward medical occurrence in a patient or clinical investigational subject who has been administered a pharmaceutical product that does not necessarily have a causal relationship with this treatment. A TEAE is an AE that is reported after a dose of study drug.

AEs are all:

- unfavorable changes in general condition
- subjective or objective signs/symptoms
- concomitant diseases or accidents
- clinically relevant adverse changes in laboratory parameters observed in a participant in the course of a clinical study

AEs comprise all disturbances of general health status, subjective and objective disease symptoms (including laboratory abnormalities), and accidents observed in the context of a clinical trial, irrespective of a possible causal relationship with the administration of the trial substance. Events occurring in the framework of a clinical trial during drug-free, and post-treatment periods, or under placebo, are also to be designated as AEs.

All AEs, whether volunteered, elicited, or noted on physical examination, will be recorded throughout the study (i.e., from screening until EOS).

Subjects will be queried for resolution of ongoing AEs or until any unresolved AEs are judged by the PI to have stabilized or if lost to follow-up. Resolution of all AEs will be promptly documented by the clinic in the subject's CRF.

Any pregnancy diagnosed during the study must be reported immediately to the investigator and sponsor, including pregnancy in female partners of male subjects. The pregnancy will be followed to term and/or outcome and this outcome must be reported to the sponsor.

Pregnancy, in and of itself, is not regarded as an AE or SAE unless the birth results in a congenital anomaly/birth defect or there is suspicion that the study treatment may have interfered with the effectiveness of a contraceptive medication or method.

8.4.2. Definition of Serious Adverse Events and SAE Reporting

An SAE is any untoward medical occurrence at any dose that results in any of the following outcomes:

- Death
- A life-threatening event (i.e., puts the subject, in the view of the PI, at immediate risk of death)
- Inpatient hospitalization or prolongation of existing hospitalization
- A persistent or significant disability/incapacity
- A congenital anomaly/birth defect
- Important medical event that may require medical or surgical intervention to prevent one of the above outcomes

An unexpected adverse drug event is any adverse drug event the specificity or severity of which is not consistent with the current IB or, if an IB is not required or available, the general investigational plan or elsewhere in the current application.

An AE is associated with the use of the drug if a reasonable possibility exists that the event may have been caused by the drug.

SAEs that are unexpected and related to either aldafermin or rosuvastatin are reportable to Regulatory Authorities. All SAEs will be reported by the PI to the sponsor and will be reported to the responsible Ethics Committee (EC) in accordance with local requirements.

The sponsor's assigned Safety Representative will be notified in writing (e.g., email or facsimile) within 24 hours of when an SAE is first recognized or reported. The Safety Representative will subsequently notify the sponsor and the sponsor's assigned Medical Monitor or designee of all reported SAEs.

Suspected statin-related AEs requiring either dose reduction or discontinuation should be reported to the third-party Medical Monitor by the PI. These subjects will be managed as outlined in [Section 8.3.17](#).

